Objectives

Primary objective

To test whether the Q_{peak} produced from the Q_{CL} protocol is not meaningfully different from the Q_{step} protocol using a non-inferiority design.

Secondary objectives

(1) to determine the reliability of the Q_{CL} and Q_{step} protocols, (2) to determine whether the VO_2 and HR obtained from the two experimental protocols are not different from the $VO_{2\text{peak}}$ and HR_{peak} obtained from the baseline $VO_{2\text{peak}}$ test, and (3) to determine whether the VO_2 measured by the Innocor is lower than the metabolic cart.

Hypothesis

We hypothesize that the Q_{CL} protocol will produce a Q_{peak} that is not different (by a margin of noninferiority of 0.5 L/min) compared to the Q_{step} protocol. A Q_{peak} of 0.5 L/min was the TE in a previous study in our laboratory (9), and is therefore deemed to be the minimum meaningful difference for determinations of Q_{peak} .

Methods

Participants

Participants will be recruited from the McMaster community and surrounding area through printed posters, web-based advertisements, and word of mouth.

Inclusion criteria:

- Adults aged 18-35 years.
- Meeting the Canadian 24-hour Movement Guidelines for Adults for aerobic physical activity, i.e. ≥ 150 minutes of moderate to vigorous activity per week (13). This will be assessed using the Canadian Society for Exercise Physiology Get Active Questionnaire (GAQ) (14).

Exclusion criteria:

- Diagnosis of any cardiovascular, respiratory, or metabolic disease that would preclude participation from a clinical standpoint, as determined by answering ‘yes’ to any of the questions on the first page of the GAQ.

Details of the experimental protocol, purpose and potential risks of participation will be explained to all participants and written informed consent will be obtained prior to participation in the study. This study has been approved by the Hamilton Integrated Research Ethics Board (Project # 13339).

Sample size determination

A calculation performed using G*Power (v 3.1.9.2) for a two-tailed dependent means (matched pairs) t-test estimated that a sample size of 34 was required to detect a medium effect size ($d_z=0.5$) with 80% power at an alpha level of 0.05 (Figure 1). A medium effect size was deemed

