This study will use a randomized within-subject crossover design. All data collection will take place in the Human Performance Laboratory at McMaster University in Hamilton, Ontario, Canada. Following preliminary screening and recruitment into the study, participants will attend the laboratory on 9 separate occasions, each separated by ≥ 48 hours (Figure 2). The first visit will involve the determination of $VO_{2\text{peak}}$ (Quark CPET metabolic cart, COSMED, Italy), HR_{peak} (Polar A3, Finland), and W_{peak} (Lode Excalibur Sport V2.0, Groningen, The Netherlands). On the second visit, participants will be familiarized with the inert gas rebreathing procedure and measurement of Q will be performed at rest and during a brief exercise test consisting of a 3-minute warm up at 50 W followed by an immediate increase to 80% of peak workload (W_{peak}) with rebreathing initiated after 2 minutes at 80% W_{peak} . The third visit will involve a verification test with the same measures as the first test. The highest values for $VO_{2\text{peak}}$, HR_{peak} and W_{peak} will be used to determine appropriate parameters and for comparative purposes with the subsequent main experimental trials. There will then be a 1-week break before beginning the experimental trials to reduce the likelihood of a testing-induced training effect. The experimental trials will consist of 6 different visits to the laboratory using a randomized repeated measures design (Experimental trials, Figure 2). Participants will perform the Q_{CL} protocol on 2 separate occasions and the Q_{step} protocol on 2 separate occasions. Q_{peak} (Innocor, COSMED, Italy) and HR_{peak} (Polar) will be assessed during each of these visits. On an additional 2 visits, participants will perform the Q_{CL} (one visit) and Q_{step} protocols (one visit) with VO_2 measured in place of Q_{peak} using the same metabolic cart as the one used for the baseline $VO_{2\text{peak}}$ test (Quark CPET metabolic cart, COSMED, Italy). These tests are referred to as $VO_{2\text{CL}}$ and $VO_{2\text{step}}$ in Figure 2. All 6 experimental trials will be randomized for each participant. The first Q_{CL} and the first Q_{step}

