test will be used to compare Q_{peak} *between* protocols, and the values obtained from the first vs the second Q_{CL} and Q_{step} tests will be used to determine the TE *within* each protocol. The VO_{2peak} from the VO_{2CL} and VO_{2step} protocols will be compared to the VO_{2peak} from the baseline VO_{2peak} test.

Participants will be instructed to maintain their habitual diet between testing sessions and abstain from strenuous exercise and alcohol consumption for a minimum of 24 hours before testing. A 24-hour dietary log will be completed before every experimental trial testing session.

Participants will be instructed to arrive to the laboratory hydrated. Testing sessions will take place at the same time of day ± 1 hour for each participant. All exercise protocols will use a cycle ergometer (Lode Excalibur Sport V2.0, Groningen, The Netherlands).

[figure not shown]

Figure 2: Schematic of study design. Q fam., cardiac output familiarization; Verif, Verification; h, hours. Each set of 2 experimental trials will be performed in random order.

Randomization

The order of the 6 experimental trials will be determined using simple randomization in Microsoft Excel. For each participant, a random, 15 decimal place number between 0 and 1 will be assigned to each experimental trial using the “=rand()” formula. The experimental trials will

be sorted using the “sort largest to smallest” function to determine the order in which the trials will be performed. The random sequence generation will be performed by a study investigator who is not involved in participant enrollment and will inform the other investigators of the order of experimental trials for each participant 24 hours before their first session. Due to the nature of the experiments, we are unable to blind the participants or researchers to the order of experimental tests; however, we will limit performance bias by blinding participants to the study hypotheses.

Primary outcome measure

Q_{peak} determined using the first Q_{CL} and Q_{step} protocols.

Secondary outcome measures

Reproducibility of Q_{peak} for each of the two IGR protocols based on the 1st and 2nd experimental trial for each test.

HR_{peak} determined during to the two IGR protocols.

$VO_{2\text{peak}}$, HR_{peak} , and W_{peak} determined during the baseline and verification $VO_{2\text{peak}}$ tests.

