A two-tailed paired samples t-test will be performed to compare each of Q_{peak}, HR_{peak}, and W_{peak} between the two experimental conditions (Q_{CL} vs Q_{step}). A two-tailed paired samples t-test will be performed to compare each of VO_{2peak}, HR_{peak}, and W_{peak} between the baseline and verification VO_{2peak} tests, to compare Q_{peak} between the first and second Q_{CL} and Q_{step} tests, and to compare VO_{2peak} between the VO_{2peak} test and each of VO_{2CL} and VO_{2step}. Significance will be set to p<0.05. Effect sizes will be reported as Cohen's d_z and 95% confidence intervals (CI) will also be determined. Q_{peak} estimated by the Q_{CL} protocol will be considered noninferior to the Q_{step} protocol if the 95% CIs for the change in Q_{peak} fall within the margin of noninferiority (i.e., 0.5 L/min) (18, 19).

Reliability of each experimental protocol and of the VO_{2peak} tests will be calculated as the TE using the following formula (20):

$$TE = (SD_{diff} \div \sqrt{2} \div grand\ mean) \times 100$$

Where SD_{diff} is the standard deviation of the difference scores between the 2 measurements, and the grand mean is the mean of all measurements included in the analysis. The TE will be expressed as a percentage.

Perspectives and significance

IGR provides a noninvasive method for determining Q_{peak} , and assessing potential changes elicited by acute and chronic exercise interventions. The proposed work will systematically compare two methods for determining IGR-derived Q_{peak} , to assess potential differences between protocols as well as reliability of each method. This research will provide novel comparative data and inform decisions by researchers regarding choice of Q_{peak} protocol in future studies.

Strategies to reduce bias

Selection bias

The order of experimental trials will be randomized for each participant using Microsoft Excel by an investigator not involved in participant enrollment. This investigator will inform the other investigators of the trial order after baseline testing, and 24 hours before the first experimental trial for each participant. The investigator performing the randomization will play a secondary role in data collection.

Performance and detection bias

Given the distinct nature of each experiment, it is not possible to blind investigators or participants to the order of experimental trials. However, we will limit performance bias by blinding participants to the study hypotheses.

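### Text and Figure 2 caption give different randomisation units, and test order is neither balanced nor in the primary analysis: a cost in precision, not a systematic bias

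*Protocol*

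**What the plan says.** **Order of trials.** Experimental procedures states: "All 6 experimental trials will be randomized for each participant". The Randomization section agrees: "The order of the 6 experimental trials will be determined using simple randomization in Microsoft Excel". It gives each of the six trials a random number and sorts on it, separately for each participant. The Figure 2 caption says instead: "Each set of 2 experimental trials will be performed in random order". The figure itself is not available here, so what forms a set of two cannot be checked.

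**Balance.** Neither section restricts the orders so that each protocol comes first equally often.

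**Primary comparison.** The primary outcome is "Q_{peak} determined using the first Q_{CL} and Q_{step} protocols". The Statistical analysis section fixes the test: "A two-tailed paired samples t-test will be performed to compare each of Q_{peak}, HR_{peak}, and W_{peak} between the two experimental conditions". It adds a 95% CI that is set against a 0.5 L/min margin. No period, visit or order term is named.

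**Effects of repeated testing.** A one-week break comes before the six trials, "to reduce the likelihood of a testing-induced training effect".

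**The concern.** The caption and the text differ in the unit that is randomised. That decides how many visits separate the two tests in the primary comparison, and how many separate the repeats behind the typical error. An analysis plan cannot settle which order is run, so the Protocol has to.

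The second issue is efficiency. Each participant makes six exercise visits. If Q_peak changes with repeated testing, through learning, training or fatigue, each paired difference carries that change with a sign that depends on which protocol came first. With unrestricted randomisation and no order term, the change adds to the SD of the differences. In any one trial it also leaves a residual shift if one protocol happens to come first more often. The break before the trials shows that the investigators thought such an effect possible.

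**Working it through.** **1. The plan's own figure.** Inputs from Sample size determination: a calculation "for a two-tailed dependent means (matched pairs) t-test", dz = 0.5, 80% power, alpha 0.05; it "estimated that a sample size of 34 was required to detect a medium effect size". Noncentral t with noncentrality dz × √n: n = 34 gives 0.5 × √34 = 2.915 and power 80.8%; n = 33 gives 79.5%. So 34 reproduces. With a difference of 0.5 L/min, dz = 0.5 implies an SD of paired differences of 0.5 / 0.5 = 1.0 L/min. The standard error is then 1.0 / √34 = 0.171 and the 95% CI half-width is 0.349 L/min.

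**2. Do the two descriptions differ in practice?** Visits between the first Q_CL and the first Q_step test:

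| Scheme | Gap in visits | SD of signed gap |
|---|---|---|
| All six shuffled (720 orders enumerated) | 1 to 4; mean absolute gap 1.87; 2 or more in 56% | 2.09 |
| Sets are Q_CL/Q_step pairs | always 1 | 1.0 |
| Sets are the two repeats of one protocol, set order random | 2 or 4 | 2.83 |

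The two set readings are assumptions, because the figure is missing. The mean signed gap is zero under the full shuffle. Under that shuffle, both tests of one protocol precede both of the other in one third of orders (2 of the 6 equally likely arrangements of two Q_CL and two Q_step tests).

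**3. Chance of imbalance at n = 34.** Which protocol comes first is Binomial(34, 0.5).
- Exactly 17:17: C(34,17) / 2^34 = 13.6%.
- 21:13 or worse, either direction: 23.0%.
- 22:12 or worse, either direction: 12.1%.

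**4. Shift in one unlucky draw.** Let π be the change from the earlier to the later of the two tests. The Protocol gives no value, so 0 to 0.5 L/min is assumed. At a k:(34 − k) split the mean difference moves by π × (2k − 34) / 34. At 21:13 the factor is 8/34 = 0.235, so π = 0.1, 0.2 or 0.5 gives 0.024, 0.047 or 0.118 L/min. If the effect is instead a linear drift of 0.1 L/min per visit, the chance shift has SD 0.1 × 2.09 / √34 = 0.036 L/min.

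**5. Validity of the unadjusted analysis.** Simulation: 100,000 trials of 34, residual SD 1.0, order drawn independently per participant. For π from 0 to 1.0 L/min, the one-sided error at the margin was 2.5% to 2.6% and CI coverage 94.8% to 95.1%. Among trials with a 21:13 split favouring Q_CL, the error was about 4.5% (π = 0.2) or 6.3% (π = 0.5).

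**6. Power.** True difference 0; success if the lower 95% bound is above −0.5 L/min, the rule in the Summary of analysis plan. Unadjusted, the SD of the differences becomes √(1 + π²). At π = 0.5 that is 1.118 and the standard error is 0.192.

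| Assumed π (L/min) | As planned | 17:17, no order term | 17:17 with order term |
|---|---|---|---|
| 0 | 80.7% | 81.1% | 81.0% |
| 0.2 | 79.2% | 79.7% | 80.8% |
| 0.5 | 71.8% | 73.7% | 80.8% |

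Most of the gain comes from the order term rather than from balance.

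**The case against.** Four arguments weigh against this point.

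- **The caption may simply be loose.** Both operational passages agree on a full shuffle of six, and only a caption differs. This stands: a second intended design is not established. The wording still conflicts and has to be made one.
- **Randomisation already deals with order.** A reader might infer that order imbalance biases the primary contrast. It does not. Order is drawn independently for each participant, so its effect has expectation zero, and its variation is already in the SD of the differences and so in the CI. Step 5 of the working confirms this. The conditional error rates describe unlucky draws only.
- **The order effect may be small.** Two maximal tests, a familiarisation visit, the one-week break, 48-hour spacing, active participants and standardised conditions all work against it. The Protocol aims to make a training effect less likely; it does not predict one across the six trials. This stands. At 0.2 L/min or less the loss of power is under 2 percentage points. An effect of 0.5 L/min would equal the whole margin and is the upper end of the assumed range.
- **Typical error.** A reader might also infer that order inflates typical error differently in the two protocols. Under the full shuffle, both have the same distribution of gaps between repeats, so no systematic difference is expected.

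An order term might also appear in an analysis plan that is not shown. The Protocol, however, does fix the paired t-test.

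**Conclusion.** The point holds in a limited form. The caption and the text must be reconciled. Order is not balanced by design, and the stated primary analysis does not use it. The planned test and CI remain valid over the randomisation, so the consequence is lost precision and a possible chance shift, not systematic bias.

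The size depends on an order effect that the document does not give: no loss at 0, under 2 percentage points of power at 0.2 L/min, and about 9 points at 0.5 L/min. These figures assume a residual SD of 1.0 L/min before any order effect is added, 34 completers and the lower-bound rule. If the 1.0 L/min already contains order variation, the planned power stands and adjustment would be a gain on top of it. This is a modest matter, worth correcting because the correction is cheap.

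**What to change.** 1. State one randomisation scheme, in the same terms, in Experimental procedures, Randomization and the Figure 2 caption. If sets of two are meant, define them.
2. Issue the orders in mirrored pairs: draw one random order, then give the next participant the same order with the Q_CL and Q_step labels swapped (and likewise the two VO2 trials). Swapping reverses the signed visit gap, so 17 pairs balance both first-protocol order and a linear drift at n = 34, apart from dropouts.
3. In place of the plain paired t-test, estimate the primary Q_CL minus Q_step difference and its 95% CI adjusted for order. Either regress the paired difference on order coded +½ and −½, or on the signed visit gap, and read the intercept; or fit a mixed model with a visit term. Keep zero as the balanced point: if the covariate is centred on the sample mean, the intercept returns the unadjusted mean and any imbalance stays in it. The unadjusted analysis can be kept as a sensitivity analysis.

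Cost: one rule in the spreadsheet, one model term and one degree of freedom (32 instead of 33), with no extra participants or visits. The second order in each pair is more predictable. That matters little, since every participant does every trial and the order cannot be blinded.

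### The primary Q_peak comparison uses only the first test of each protocol, so its confidence interval is wider than the planned data allow

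*Protocol*

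**What the plan says.** Under Experimental procedures, the protocol schedules six experimental visits in random order. Four of them yield Q_peak: "Participants will perform the Q_{CL} protocol on 2 separate occasions and the Q_{step} protocol on 2 separate occasions". The same section assigns the first test of each protocol to the between-protocol comparison, while "the values obtained from the first vs the second Q_{CL} and Q_{step} tests will be used to determine the TE" within each protocol. The heading Primary outcome measure repeats the restriction: "Q_{peak} determined using the first Q_{CL} and Q_{step} protocols". Statistical analysis adds paired t-tests of first against second tests. The document gives no reason for leaving the second tests out of the primary contrast.

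Under Sample size determination, a calculation for a "two-tailed dependent means (matched pairs) t-test" "estimated that a sample size of 34 was required to detect a medium effect size" (d_z = 0.5) "with 80% power at an alpha level of 0.05". The hypothesis is framed "by a margin of noninferiority of 0.5 L/min". The decision rule has two wordings. Statistical analysis asks for the 95% CI to fall within the margin, while the Summary of analysis plan looks only at the lower bound.

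**The concern.** Noninferiority here is decided by where a confidence interval falls relative to 0.5 L/min, so the width of that interval largely determines whether the study can conclude anything. Each participant contributes two measurements per protocol, but the interval is built from one of each. The second pair estimates the same mean protocol difference with fresh measurement error. Averaging would shrink the test-retest part of the variance at no cost in visits.

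An order or learning effect does not obviously justify preferring the first tests. The order of all six trials is randomised, and two ramp tests and a rebreathing familiarisation visit come before them. At stake is the chance that a Q_CL protocol which really is comparable fails to be shown so, when data already planned could have shown it.

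**Working it through.** **Inputs from the protocol**
- n = 34, d_z = 0.5, two-sided alpha 0.05, power 80% (Sample size determination).
- Margin 0.5 L/min (Hypothesis).
- Typical error (TE) of Q_CL: 0.5 L/min (Hypothesis) and 4.7% (Background and rationale).
- TE of step tests: about 7% (Background and rationale).
- Two Q_peak tests per protocol per participant (Experimental procedures).

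**Assumptions, not stated in the protocol**
- SD of the single-test paired difference = margin / d_z = 0.5 / 0.5 = 1.0 L/min.
- The mean Q_peak implied by the two Q_CL figures is 0.5 / 0.047 = 10.6 L/min, so 7% for Q_step is 0.07 × 10.64 = 0.74 L/min.
- Errors are independent between visits, the true difference is 0 and there is no dropout.

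**Step 1: the plan's own figure.** Exact noncentral-t power for a paired t-test with d_z = 0.5 and two-sided alpha 0.05 first reaches 80% at n = 34, where it is 0.808. The stated sample size reproduces.

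**Step 2: variance of the contrast.** Let V be the variance due to true participant-by-protocol differences.
- One test each: V + TE_CL² + TE_step² = 1.0.
- Mean of two tests each: V + (TE_CL² + TE_step²)/2 = 1.0 − (TE_CL² + TE_step²)/2.

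With the numbers put in:
- TE 0.5 for both: 1.0 − (0.25 + 0.25)/2 = 0.75, so SD = 0.87.
- TE 0.5 and 0.74: 1.0 − (0.25 + 0.555)/2 = 0.598, so SD = 0.77.
- TE 0.3 for both (an assumed low value): 1.0 − (0.09 + 0.09)/2 = 0.91, so SD = 0.95.
- All variance is test-retest error (V = 0): 0.50, so SD = 0.71.

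**Step 3: interval width and power at n = 34.** The half-width is t(0.975, 33) × SD/√34 = 2.035 × SD/5.831. Lower-bound power is one-sided 0.025 noncentral-t with noncentrality (0.5/SD)√34. Whole-interval power (95% CI entirely within ±0.5 L/min) was simulated with 400,000 runs.

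| Primary data | SD (L/min) | CI half-width (L/min) | Power, lower bound | Power, whole CI |
|---|---|---|---|---|
| First tests only | 1.00 | 0.35 | 0.81 | 0.62 |
| Means, TE 0.3 both | 0.95 | 0.33 | 0.84 | 0.69 |
| Means, TE 0.5 both | 0.87 | 0.30 | 0.90 | 0.81 |
| Means, TE 0.5 and 0.74 | 0.77 | 0.27 | 0.955 | 0.91 |
| Means, V = 0 (limit) | 0.71 | 0.25 | 0.98 | 0.96 |

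**Step 4: sensitivity to the assumed SD.** With TE 0.5 for both and a single-test SD between 0.75 and 1.5 L/min, lower-bound power rises by 3 to 10 points: 0.965 to 0.999 at SD 0.75, 0.81 to 0.90 at SD 1.0, and 0.47 to 0.52 at SD 1.5.

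**Step 5: sensitivity to a true difference of zero.** If Q_CL truly read 0.1 L/min lower (an illustrative assumption), the noncentrality becomes (0.4/SD)√34. Lower-bound power is then 0.62 with first tests and 0.74–0.83 with means at SD 0.87–0.77.

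**The case against.** First-versus-first is prespecified, stated consistently, unbiased under the randomised order, and powered as claimed under the lower-bound rule. It also matches how a single test would be used in practice. All of that stands, and it is why this is a matter of efficiency.

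Several stronger readings are tempting but not supported:
- *Half the Q_peak data are thrown away.* They are not. The second tests carry the first secondary objective, reliability, and the first-versus-second comparisons. They are idle only for the primary question.
- *Power would go from 81% to 98%, as if 68 participants had been enrolled.* This needs all of the 1.0 L/min SD to be test-retest error, that is, error variances summing to 1.0. The protocol's own typical errors give 0.50 to 0.80.
- *Power would go from 62% to 96%.* This needs the same extreme assumption and also the whole-interval reading of the decision rule. The two wordings of that rule are a separate matter and should not be used to enlarge this one.
- *A failed first measurement loses the participant.* The protocol does not say how such a case is handled, and that is commonly left to the statistical analysis plan.

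One further objection is that averaging changes the question. It does so only if the protocol difference itself shifts between first and second tests. The protocol does mention a possible testing-induced training effect, but it sets a one-week break to limit it. Retaining first-versus-first as a sensitivity analysis covers what remains.

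**Conclusion.** The point holds as an avoidable loss of precision in the primary analysis. Using the protocol's own typical errors, averaging both tests narrows the deciding interval by about 13–23% (0.35 to 0.30–0.27 L/min). It adds roughly 10 to 15 points of lower-bound power to a base that already meets its target. The benefit is larger, about 19 to 29 points, if the whole interval must lie within the margin, because first tests alone then fall short of 80%.

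The size rests on an SD of 1.0 L/min inferred from the margin and d_z, and on typical errors from earlier studies carrying over to this sample. The protocol does not state how much of the SD is test-retest error. If that share is small, so is the gain (0.81 to 0.84 with TE 0.3 L/min). A reader might infer that the study is biased or underpowered as planned. Under the lower-bound rule and a true difference of zero, the document does not support either inference.

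**What to change.** Under Primary outcome measure, Experimental procedures and Statistical analysis, define the primary contrast as each participant's mean of the two Q_CL tests minus the mean of the two Q_step tests, with its 95% CI compared with the margin.

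A related alternative is a mixed model on all four Q_peak values, with protocol and visit number as fixed effects and participant and participant-by-protocol as random effects. It is not identical to the mean contrast: the six visits are ordered by unrestricted randomisation, so visit position is not balanced within a participant and adjusting for it will generally shift the estimate. One of the two should therefore be named in advance.

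Keep first-versus-first as a sensitivity analysis and leave the typical-error analysis as it is. The change costs wording only, with no extra visit, test or participant, and should be made before the between-protocol results are examined.
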